1.0 OBJECTIVES

The overall goal of the Skin Cancer Prevention Program Project is to employ novel technologies and develop new therapeutic strategies to prevent intraepithelial neoplasias in the skin (i.e. actinic keratosis, cutaneous squamous cell carcinoma *in situ*). Our objectives in pursuit of this goal are to determine clinical, histopathologic, and protein/phosphoprotein signaling patterns associated with human skin carcinogenesis and to develop safe, highly efficacious intervention strategies for the prevention of skin cancer. The **overall hypothesis of the project** is that Toll-like Receptor 4 (TLR4) and T-LAK cell-originated protein kinase (TOPK) / p53-related protein kinase (PRPK) drive important signaling pathways, with potential synergism to prevent cutaneous squamous cell carcinoma (cSCC), and that TOPK/PRPK and TLR4 signaling pathways are modulated in the skin by acute exposure to solar simulated light (SSL).

The aim of this study is to assess TLR4 and TOPK/PRPK signaling in sun damaged (SD) human skin acutely exposed to solar simulated light (SSL). The purpose of this aim is to assess the effect of acute UV exposure on the signaling pathways of interest in order to validate the acute clinical model prior to intervention with small molecule inhibitors. Acute UV exposure will be evaluated in SD skin to determine the level of activation of the targeted pathways using reverse-phase protein array (LCM-RPPA) analysis and immunohistochemistry (IHC). This translational aim will prospectively analyze TLR4 and TOPK/PRPK signaling pathways activation by acute exposure of human subjects to SSL at twice the minimal erythema dose (MED) for each subject. We will evaluate the modulation of key proposed signaling pathways using RPPA and IHC in acutely irradiated human skin. We will also determine the optimal time points for evaluation of biomarker modulation.

Primary Endpoint: To assess TLR4 and TOPK signaling pathway activation levels pre- and post-SSL exposure in SD skin.

Exploratory Endpoint: To assess the correlation between SD level and the magnitude of SSL-induced pathway activation.

Thirty-six (36) subjects with a broad range of SD on the forearm will be recruited. Based on the standardized clinical photodamage scale [1], we will include mild (N=12), moderate (N=12), and severely (N=12) sun damaged (SD) skin. The level of SD will be scored, using a range of 0-9, where absent SD = 0, mild SD = 1-3, moderate SD = 4-6 and severe SD = 7-9 (see Appendix C).

We will irradiate and biopsy the SD forearm skin of each healthy adult volunteer and collect skin punch biopsies before and after exposure to SSL for analysis using LCM-RPPA and IHC. The results of this study will be used to aid in design of pharmacodynamic SSL exposure studies with small molecule inhibitors in subsequent studies.

2.0 BACKGROUND, SIGNIFICANCE AND PRELIMINARY WORK

One out of three new cancers is a skin cancer, making skin cancer the most common malignancy worldwide. Approximately 4.9 million cases of non-melanoma skin cancer (NMSC) (basal cell carcinoma [BCC] and cutaneous squamous cell cancers [cSCC]) occur annually. As incidence rates for NMSC continue to rise, there is an increasing and substantial impact on morbidity and health care costs that account for \$8.1 billion/year in skin cancer treatment with the majority of these lesions representing keratinocytic neoplasms.

New technologies increasingly allow for the capacity to individualize therapeutic prevention strategies based on gene expression patterns and direct, multiplexed cell signaling profiling. Target modulations, pathway activation, skin biology alterations, and other basic science discoveries will be translated into the clinic. Increasingly, our research group has attempted to dissect solar light-induced signal transduction pathways leading to cSCC with the aim of identifying molecular targets for chemopreventive drug development. Essential to this research approach is a requirement to validate molecular targets identified in solar light-induced cSCC carcinogenesis and skin biology models. Strategies to be employed include incorporation of advanced Reverse-Phase Protein Array (RPPA) technology for analysis of protein/phosphoprotein activity and molecular network analysis, and use of immunohistochemistry (IHC) analysis from formalin-fixed paraffin-embedded tissues. These technologies will allow us to detect unique targets for the ultimate individualized treatment of IENs in the skin.

2.1 UV Signal Transduction Pathways

Ultraviolet radiation (UVR), the major etiologic factor in human skin cancer, elicits a number of biological responses in the skin that include pigmentation, erythema, and cell death [2-5]. UVR can be divided by wavelength into UVC (180-280 nm), UVB (280-320 nm), and UVA regions (UVA I, 340-400 nm; UVA II, 320- 340 nm), all of which show strong carcinogenic activity with regard to induction of squamous type tumors in mouse

skin. UVR is a complete carcinogen in that it acts as both an initiator, presumably by causing DNA damage leading to gene mutations, and as a tumor promoter. Because UVC is absorbed by the ozone layer, UVA and UVB are considered to be the major carcinogenic components of solar radiation with relevance for human skin cancer [6-13]. UVA comprises more than 95% of solar UVR and is recognized as a major contributor to carcinogenesis [14-17]. Mechanistically, UVR induces both genotoxic effects such as DNA damage and mutations as well as epigenetic events such as induction of gene expression. DNA damage is induced directly by UVR absorption in the DNA resulting in the induction of cyclobutane pyrimidine dimers (CPD), (6-4) pyrimidine dimers, cytosine photohydrates and purine photoproducts that can yield specific "signature" mutations (C to T and CC to TT) [18,19]. Longer wavelengths can indirectly induce DNA single-strand breaks and DNA-protein crosslinks through reactive oxygen species [15]. Therapeutic prevention agents that demonstrate activity toward these UVR signaling pathways will be evaluated in clinical trials.

2.2 Immunohistochemistry

The use of immunohistochemical biomarkers permits studies with smaller sample size and shorter duration compared to studies that use cancer incidence as an endpoint. To be valid, the quantitative degree and pattern of biomarkers should correlate with carcinogenic transformation or alternatively biomarkers markers may demonstrate the effect of a particular agent on a molecular pathway or biochemical processes (i.e. arachadonic acid/cyclooxygenase pathways, polyamine synthesis). This has been demonstrated by the suppression of polyamine levels in tissue treated with the polyamine synthesis inhibitor, alpha-2-(Difluoromethyl)-dl-ornithine, or DFMO [20,21].

In a previous study completed by this group, IHC was performed on samples collected at baseline, 5 min, and 1, 5, and 24 h following 2X MED of SSL on SP skin of 10 subjects; there was a significant increase in pTOPK and pPRPK activity starting as early as 5 min post SSL exposure with a sustained expression up to 24 h (**Fig. 1**). Analysis of TLR4 using the same samples also revealed increased pathway activation primarily at 24 h post-SLL exposure.

IHC assays will include pTLR4, MyD88, p-p65/NFKB, TAB2, pTOPK, p-PRPK, p-Erk, pP38, and pP90RSK. IHC assays previously established will also be performed for validation of SSL-induced changes.

[figure not shown]

Fig. 1. Comparison of p-PRPK and p-TOPK levels on sUV-exposed human skin harvested in a time-dependent manner. IHC staining was performed and representative data analyzed (30 photos from 10 subjects) for each of the following: normal human skin without sUV, 5 min post 2X MED sUV, 1 h post 2 MED sUV, 5 h post 2 MED sUV and 24 h post 2 MED sUV. Shown is expression of phosphorylated (p)-PRPK (a) and p-TOPK (b). Magnification: 400x. **Upper panels:** Phosphorylated PRPK, total and p-TOPK levels are presented as sum of the integrated optical density (IOD) values. **Lower panels:** Representative staining (brown color) is shown. The asterisks (*, **) indicate a significant difference ($p < 0.05$ or $p < 0.001$, respectively).

2.3 Mapping of Protein Signaling Networks

Reverse-phase protein array analysis (RPPA), a novel analysis for multiplexed quantitative measurement of multiple signaling proteins from biological specimens represents a novel means of measurement of hundreds of proteins, many of which are phosphoproteins, in a single biopsy specimen. This array technology is a miniaturized calibrated dot-blot immunoassay, and with over 90 peer-reviewed publications supporting the implementation of this platform (60 from the [name]/[name] laboratories), it represents one of the most widely published protein microarray technologies. Moreover, the RPPA platform is now being used within the [name] laboratories for clinical trial-based applications since it is run as a CAP/CLIA in-house developed assay, which demonstrates the maturity of the platform. With the RPPA technology, serial dilutions are printed of each sample, control or standard, to maintain sample

concentration. Each spot contains a bait zone measuring only a few hundred microns in diameter. The detection probe can be tagged and signal amplified independently from the immobilized analyte protein. Coupling the detection antibody with highly sensitive amplification systems can yield detection sensitivities to fewer than 1,000 to 5,000 molecules per spot with good linearity (correlation coefficient or $R^2 = 0.990-0.999$) and inter-experiment precision ($R^2 = 0.973$). Between run and within run analytical precision is between a 3-13% CV (coefficient of variation) [22].

Activation of proteins by phosphorylation of kinase-driven signaling networks contains information regarding the disease process as well as potential therapeutic targets [23]. The phosphorylation state of proteins can be detected and assessed using specific phospho-specific antibodies developed to recognize the phosphorylated isoform of the kinase substrates [23-25]. Each antibody undergoes extensive validation for specificity prior to RPPA analysis using peptide competition and single band detection on Western as well as ligand induction. Currently, [name] has over 300 extensively validated different cell signaling antibodies in his portfolio. Using RPPA, many dozens of kinase substrates can be quantified and measured simultaneously through multiplexed phosphospecific antibody analyses. RPPA has demonstrated sensitivity, precision and accuracy that enable the evaluation of signaling networks from a very small number of cells (e.g. procured using laser capture microdissection) from biopsy material.

3.0 EQUIPMENT INFORMATION

[figure not shown]
3.1 Solar Simulated Light Source

A Multiport UV Solar Simulator Model 600 (Solar Light Co., Inc., Philadelphia, PA) will be used to administer SSL exposures to the test areas on the skin. The device is equipped with six 8mm liquid light guides (LLG), allowing for 6 simultaneously conducted exposures. A large 3x2 endplate places the LLGs several centimeters apart and is specifically designed for SPF and photopatch testing. The dose of emission from each LLG can be precisely regulated and the spectrum of emission can be limited to UVA (320-390 nm) or UVB+UVA (290-390 nm). For added safety, the device is equipped with a power supply which stabilizes the lamp current. An operator-controlled shutter and dose control system monitor and control the delivered dose.

An automatic internal igniter minimizes the electromagnetic interference and a fan provides cooling that increases lamp life. The connection to the power supply is a 5

foot cable equipped with a quick disconnect connector. The operator can select between UVA only and a combined UVA/UVB spectrum by placement of an optical filter.

The source of radiation is a 150 Watt xenon lamp. The spectral output (indicated below) follows the distribution of sunlight from 290 to 390 nm.

4.0 SUBJECT ELIGIBILITY

4.1 Inclusion Criteria

- Healthy individuals 18 years of age or older.
- Individuals with mild, moderate, or severe photodamage [1] of the skin on the forearms (also Appendix C) and Fitzpatrick skin type II or III (21 CFR 352.72).
- Females of childbearing potential will need to undergo a pregnancy test at the enrollment visit, after administration of the ICF and before exposure to SSL. Premenopausal female subjects must use an effective method of birth control (such as oral contraceptives, consistent use of barrier contraceptives, IUD, or other proven method of birth control) during study participation. For the purposes of this study, a woman will be considered postmenopausal if any of the following criteria are met: (1) she has had prior bilateral oophorectomy; (2) she is over the age of 60 years; or (3) she is under the age of 60 years and has not had a menstrual period in 12 or more months in the absence of chemotherapy, tamoxifen, toremifene, or ovarian suppression.

- Individuals who are willing to limit sun exposure to the body during the study period and who agree to wear protective clothing when they are outdoors.
- Individuals who have the ability to understand and willingness to sign an informed consent before initiation of study procedures, after the nature of the study is explained to them and they have had the opportunity to ask any questions.

4.2 Exclusion Criteria

- Individuals with any inflammation or irritation of the skin at the test areas, or any skin conditions felt by the study medical provider to contraindicate enrollment. This includes, but is not limited to, psoriasis or atopic dermatitis within the test areas.
 - Test area is defined as the 6 mm areas of skin that is exposed to SSL and will be biopsied.
- Individuals with a history of any untreated skin cancer, melanocytic lesions, or actinic keratoses in the test areas are ineligible. History of such conditions at a body site other than the test areas is not exclusionary if in the opinion of the study medical provider it will not pose a risk to the subject.
- Individuals who have had invasive cancer, chemotherapy or radiation therapy within five years of study enrollment
- Individuals who are immunosuppressed by virtue of medication or disease. This includes AIDS patients, subjects taking oral steroids, and subjects on immunosuppressants/immunomodulators (cyclosporine, chemotherapeutic agents, or biologic therapy), as determined by the examining study medical provider.
- Individuals with serious intercurrent illness including, but not limited to, ongoing or active infection, psychiatric illness, or other situations that in the opinion of the examining study medical provider would limit compliance or interfere with the study regimen.
- Individuals who have used photosensitizing drugs (see Appendix for examples) within 30 days of enrollment, or who will be using a photosensitizing drug during the time of the study, will not be eligible.

Subjects may be reconsidered for eligibility 30 days after the last dose of such medications.

- Individuals who have used any topical medication other than emollients or sunscreen/sunblock on the test area within 30 days prior to study enrollment. If a study participant requires topical medication to the test area during the study, they will be withdrawn from the study.
- Individuals who have used retinoids, steroids, 5-fluorouracil, Levulan, Vaniqua (eflornithine), Solaraze, or Imiquimod (Aldara®) anywhere on the body within 30 days prior to study enrollment. Subjects may be reconsidered for eligibility 30 days after the last topical treatment with such medications.
- Individuals must not take mega-doses of vitamins. Mega-doses are defined as more than 5 capsules of standard multivitamins daily or more than the *Tolerable Upper Intake Levels of Vitamins*, as defined by the Institute of Medicine, National Academy of Sciences. Such vitamin therapy must be discontinued at least 30 days prior to study entry.
- Individuals with a history of deliberate natural or artificial sun exposure (tanning) within 30 days of study enrollment are not eligible.
- Individuals with Fitzpatrick skin type I are ineligible, as the proposed SSL dose could result in a burn of greater than mild severity.
- Individuals with Fitzpatrick skin type IV, V or VI are ineligible, as they are unlikely to exhibit a salient response in the proposed design.
- Individuals currently enrolled in or who plan to enroll in another clinical trial. There must be a 30-day period between completing a previous study and enrolling in this study.
- Individuals with a known allergy to lidocaine are not eligible.
- Females who are pregnant or nursing.

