5.0 PRE-STUDY REQUIREMENTS

Pre-study requirements include:

- Administration of the screening consent and HIPAA authorization form;
- Eligibility screening by a study medical provider, including a skin examination and a review of the subject's medical history, concomitant medications, and supplements;

- Subjects must have mild (N=12), moderate (N=12), or severe (N=12) sun damage [1] of the skin on the forearms (Appendix C).

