6.2 Trial Schema

Informed consent will be administered to all study participants. Female participants of childbearing potential will undergo a urine pregnancy test prior to SSL exposures. If there is a scheduling issue, a pregnancy test will be repeated if ≥ 7 days elapse between MED determination and the administration of SSL at 2X MED for biopsy. Each study participant will act as his/her own control. Areas to be used for baseline biopsies, MED (minimal erythema dose) determination, and study biopsy sites will be marked on the participant's skin with non-permanent surgical marking ink.

MED will be determined on the left buttock. After the MED of the subject is determined, three biopsy sites will be outlined on the left forearm. Then SSL at a dose of 2X MED will then be administered at two of the biopsy sites on the left forearm. Skin punch biopsies will then be collected at 1 hour (± 15 minutes) and 24 hours (± 2 hours) post-SSL exposure. In addition, one 6mm skin punch biopsy sample will be collected from the left forearm at baseline to serve as an unexposed (SSL) control sample. The control sample will be collected from a site that is at least 6 cm away from the sites exposed to SSL. All of the biopsy samples will be collected as close to the exact target time as possible. Photographs will be taken of the left forearm prior to skin punch biopsies. Study participants will return for suture removal and follow-up from 10 to 16 days after the final biopsies are collected, and they will be followed for as long as necessary if complications occur. Study participants may have their sutures removed by an outside provider per their preference.

Table 1 Outline of Trial Schema (n = 36)

Screening	Informed Consent Form and HIPAA authorization form administered; Skin examination and medical history reviewed by study provider
Visit 1*	Urine pregnancy test if necessary; SSL exposures administered for MED determination to left buttock.
Visit 2	MED visually determined
Visit 3*	Photograph of left forearm will be taken; SSL to 2 biopsy sites on left forearm at a dose of 2X MED; Biopsy collected from control biopsy site (no SSL) on left forearm; Biopsy collected from 1-hour test site on left forearm.
Visit 4	Photograph of left forearm will be taken; Skin biopsy collected from left forearm at 24 hours after SSL exposure
Visit 5**	Sutures removed 10-16 days after Visit 3

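### Does the section 4.2 definition of test area leave the unexposed control biopsy site open to diseased or treated skin?

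*Combined protocol and SAP*

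**What the plan says.** Section 4.2 defines the term under its first exclusion: "Test area is defined as the 6 mm areas of skin that is exposed to SSL and will be biopsied". Three exclusions in that section rely on it:

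1. Inflammation or irritation at the test areas. The same criterion also covers "any skin conditions felt by the study medical provider to contraindicate enrollment", with no limit to the test areas.
2. Untreated skin cancer, melanocytic lesions or actinic keratoses in the test areas, with a carve-out: "History of such conditions at a body site other than the test areas is not exclusionary", provided the provider sees no risk to the subject.
3. "Individuals who have used any topical medication other than emollients or sunscreen/sunblock on the test area within 30 days prior to study enrollment". A companion sentence on withdrawal uses the same term: "If a study participant requires topical medication to the test area during the study".

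A separate criterion bars a list of named topical agents "anywhere on the body within 30 days prior to study enrollment".

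Section 5.0 requires "Eligibility screening by a study medical provider, including a skin examination". Section 6.2 then says: "After the MED of the subject is determined, three biopsy sites will be outlined on the left forearm". Two of those sites receive SSL. The third is the unexposed control, on the same forearm and at least 6 cm from the others. Section 8.1 compares unexposed baseline samples with the 1 h and 24 h samples.

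**The concern.** The definition joins two conditions, exposed and biopsied, and the control meets only the second. Read literally, a subject could have an actinic keratosis, a patch of dermatitis or a recently treated spot at the control site and breach none of the three site-specific criteria. No other passage expressly requires that site to be clear.

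The control matters more than either irradiated sample taken singly. Each subject has one, and it enters both the 1 h and the 24 h fold change. A control with raised signalling would hide activation at both time points, and one with lowered signalling would exaggerate it. The wording would then guard the two exposed samples and leave unguarded the one they share.

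**Working it through.** **Scope of the literal gap.** Section 6.2 gives three biopsy sites, of which two are exposed: 3 − 2 = 1 site outside the definition. Three exclusions in section 4.2 use the term.

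**Can the gap operate?** Setting the sections in time order:

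- *Screening (sections 5.0 and 6.1).* A medical provider examines the skin, reviews medications and verifies eligibility before enrollment.
- *MED reading (section 6.3.5).* This takes place 22 to 26 hours after the buttock exposures.
- *Site outlining (section 6.2).* The three forearm sites are outlined only after the MED is known.

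Even if screening is combined with Visit 1, as the footnote to Table 1 allows, the sites are outlined about a day later. At screening nobody can say which 6 mm spot will be the control. A site-specific criterion can be applied then only by judging the forearm skin from which all three punches may come.

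**What remains, criterion by criterion.**

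| Exclusion | Literal gap at the control site | What narrows it |
|---|---|---|
| Inflammation or irritation | The mandatory part misses it | The provider's discretion is not limited to test areas |
| Skin cancer, melanocytic lesion, actinic keratosis | Misses it | Body site may mean another anatomical region, not another point on the same forearm |
| Topical medication within 30 days | Misses it | The named agents are barred body-wide, so only other topicals applied to the control spot alone escape |

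Diffuse disease or a widely applied topical would usually reach an exposed site too. Only a focal abnormality confined to the control escapes, and staff would have to choose that spot for the punch.

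**How the documents use the term.** The 6 mm in the definition is the punch diameter common to all three biopsies (section 7.1), not the 8 mm light guide (section 3.1). Table 2 lists the control under its *Test Site* column. Table 1 separates the control site from the 1-hour test site, and section 6.3.2 uses *test areas* for the buttock. This is loose usage. It does not show a deliberate exemption for the control.

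**Later checks.** Section 6.2 has the left forearm photographed before the punch biopsies, and Table 2 assigns histology to every biopsy, control included. An inflamed or keratotic control would probably show, although no rule says what would follow.

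**Size, for illustration.** Assume the estimator is the mean log2 fold change; section 8.1 mentions log2 fold change only in its power statement. Let *k* of *n* controls be raised by *d* log2 units. Then

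shift in mean = −(*k*/*n*) × *d*.

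Section 8.1 gives *n* = 30 evaluable (36 × 0.85 = 30.6). The documents give neither *k* nor *d*, so both are assumed:

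| *k* | *d* = 0.5 | *d* = 1 | *d* = 2 |
|---|---|---|---|
| 1 | −0.017 | −0.033 | −0.067 |
| 3 | −0.050 | −0.100 | −0.200 |
| 5 | −0.083 | −0.167 | −0.333 |

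With the 80% completion in section 6.1, 36 × 0.80 = 28.8, and one control counts 1/28.8 = 0.035 instead of 0.033. The difference between 1 h and 24 h is unaffected because the control cancels: (Y₁ − C) − (Y₂₄ − C) = Y₁ − Y₂₄. The 1/*n* dilution holds for any single outlying value, so the table shows scale only and is no evidence that the wording causes bias.

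**The case for a change.** The strongest case rests on the lesion criterion. There the text is not merely silent. It permits lesions away from the test areas, and its proviso concerns risk to the subject, not validity of the sample. The trial enrols subjects with severe forearm sun damage, and section 1.0 names actinic keratosis among the neoplasias the program aims to prevent, so a focal lesion on the forearm is plausible. Clear skin at the exposed sites does not establish clear skin 6 cm or more away. The provider's discretion is framed around suitability for enrollment, and nothing directs it to the comparator. Within one severity level the dilution is also weaker: 12 planned, or 12 × 30/36 = 10 evaluable if dropout is even, so one control counts 1/10 in the exploratory severity analysis.

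The literal reading stands, and so does the absence of any express requirement for a clear control site. Several affected controls would not be negligible. What does not follow is that the plan would produce them. That needs staff who outline sites on skin they have examined to put the punch on a visible lesion, and nothing in the documents suggests they would.

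Rewording has its own difficulty. Naming the three biopsy sites in the eligibility criteria would refer to sites not yet chosen at screening. Changing only the pre-enrollment topical sentence would part it from the withdrawal sentence beside it. Redefining the term throughout would reach the serious adverse event definition in section 12.2.

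**Conclusion.** No change to the plan follows. The definition is carelessly worded, and read literally it misses the control biopsy in three exclusions. The order of procedures, the body-wide ban on named topicals, the provider's discretion and the choice of sites by study staff leave the omission almost nothing to act on. It is a drafting slip that staff would apply sensibly, and correcting it would not be expected to alter any result.

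No bias or loss of power is shown. The documents give no standard deviation, effect size or rate of abnormal controls, so none can be derived. On the assumed estimator, an isolated case would be diluted thirty-fold in the primary means. The conclusion assumes that the screening examination covers the candidate forearm skin and that sites are not placed on visibly abnormal spots. If several control biopsies proved abnormal on histology, the point would deserve another look.
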